5.1 Type of Trial

...

Treatment duration is approximately 6 months in the on-demand arm and from approximately 7 (200 days plus screening period of 2-3 weeks) to approximately 19 months in the prophylaxis arm. The maximum treatment period in the Main Phase of this trial is *approximately 27 months*. In the prophylaxis arm, all patients will continue in the Main Phase until the last patient initiated in the prophylaxis arm has received at least 50 EDs of N8-GP (*except for patients having had surgery as part of pathfinderTM 3*), thus all patients in the prophylaxis arm will receive at least 50 EDs of N8-GP and the average exposure to N8-GP will be more than 1 year.

...

In the part 2 patients can continue being on prophylaxis but can change between *every 4 or 7 day dosing regimens in accordance with the rules described in section 5.3.1* ~~according to their bleeding episode pattern.~~

5.2 Rationale for Trial Design

...

Part 2 of the Extension Phase will consist of a single prophylaxis treatment arm where it will be possible to ~~individualise~~ *change between every 4 day or 7 day treatment in accordance with the rules described in section 5.3.1* ~~according to recommended guidelines (see section 5.3) taken the patients bleeding pattern into account.~~

5.3.1 Prophylaxis

...

Other changes of the dose or dosing interval for prophylaxis are not allowed within *the main phase of the trial*. However, extra doses of N8-GP will be administered if a patient experiences a treatment requiring bleeding episode or in case of minor surgery.

Extension Phase part 1: The prophylaxis dose of N8-GP is administered in the non-randomised group every 4 days or in the randomised group every 4 day or every 7 day depending on which treatment arm the patient is allocated to. Based on the bleeding pattern, the Investigator may change the every 7 day prophylaxis treatment to an every 4 day treatment regimen (the non-randomised arm) *at any time*. ~~but~~ Changing vice versa is not permitted. *In addition the Investigator must monitor the patient on an on going basis and change patients from every 7 day prophylaxis treatment to an every 4 day treatment regimen in accordance with the following rule. A patient on every 7 day prophylaxis must be switched back to every 4 day prophylaxis if either of the following criteria are met over a 8 week period:*

- *Two or more spontaneous bleeding episodes*
- *One severe bleeding episode requiring hospitalisation.*

Novo Nordisk will monitor that patients are switched from the every 7 day prophylaxis treatment to an every 4 day treatment regimen adhering to the rule mentioned above. Novo Nordisk will furthermore monitor the number of patients switching from every 7 day to every 4 day treatment regimen and will terminate the 7 day treatment arm if the below rule is met:

- *If at least 15 out of 30 patients (or 50% of 30 or more) whom have been randomised to the every 7 day treatment arm are switched back to the every 4 day treatment arm, then the every 7 day treatment arm will be closed and all remaining patients will be switched to every 4 day treatment.*

...

Extension Phase part 2: During this period it is possible to ~~adjust~~*change* the prophylaxis treatment of patients to *every 4 day or 7 day treatment*~~an individualised regimen. Treatment regimens ranging from once weekly to every 4 day will be allowed: every 4 day, every 5 day, every 6 day or every 7 day.~~ For deciding to change a regimen it is strongly recommended to follow *the Investigator must monitor the patient on an on going basis and follow the below* ~~guidelines~~*rules for change of regimen:*

- *0-2 bleeding episodes within last 6 months on same regimen would allow a less frequent dosing interval to a lowest frequency of every 7 day. Change to a less frequent treatment regimen should be done while the patient is at a site visit*
- *If a patient on every 7 day treatment regimen over a 8 week period experiences two or more spontaneous bleeding episodes or one severe bleeding episode requiring hospitalisation, then the patient must be switched back to every 4 day treatment regimen* ~~3 or more bleeding episodes within last 6 months on same regimen allows to stay on regimen or change to a more frequent regimen to a highest frequency of every 4 day~~
- ~~Change of regimen can only take place after being on the same regimen for at least 6 months~~

Clinical judgement has to be applied in order to avoid increased risk to the subject's safety and must always overrule ~~guidelines~~ *the above described rules* when deemed necessary by the Investigator.

The dose for the Extension Phase part 1 and 2 will be:

50 U/kg BW of N8-GP for prophylaxis treatment every 4 day

~~60 U/Kg BW of N8-GP for prophylaxis treatment every 5 and 6 day~~

75 U/Kg of N8-GP for prophylaxis treatment every 7 day

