6.5 Withdrawal Criteria

The patient may withdraw at will at any time.

The patient may be withdrawn from the trial at the discretion of the Investigator due to a safety concern or if judged non-compliant with trial procedures.

A patient must be withdrawn if the following applies:

1. Haemostasis not achievable with N8-GP: The bleed cannot be controlled after 48 hours using adequate doses of N8-GP
2. FVIII inhibitor (≥ 0.6 BU/mL) as confirmed by re-testing by Central Laboratory
3. Allergy/anaphylaxis to the trial product
4. Use of Coagulation Factors: FVIII, FIX and FVII-containing products other than N8-GP and other FVIII-containing products like fresh frozen plasma or cryoprecipitate. (**Exception:** current FVIII allowed until 72 hours before Visit 2a)
5. Incapacity or unwillingness to follow the trial procedures

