2.6 Section 5 Trial Design

5.1 Type of Trial

This phase 3 trial is a multi-centre, multi-national, open-label, non-randomised trial evaluating safety, pharmacokinetics and clinical efficacy of N8-GP when used for treatment of bleeding episodes and for long-term prophylaxis. The trial consists of a Main Phase followed by an Extension Phase.

A minimum of 115 (155) (see section 18.5) patients must complete the trial including at least 10 patients in on-demand treatment and 105 (145) (see section 18.5) patients in prophylaxis treatment

with N8-GP every 4 days *in the Main Phase of the trial*. In order to ensure recruitment of patients for PK it is planned that the first patients (approximately 10) entering the prophylaxis arm must undergo PK sessions. Whether a patient will receive prophylaxis treatment or on-demand treatment is non-randomised and will be the choice of the patient and Investigator. This will be based on medical needs and decided at the Screening visit. For the US, recruitment will open for the on-demand arm before enrolling patients in the prophylaxis arm, whereas both arms will open concurrently at non-US sites.

The distribution of patients *in the Main Phase of the trial* will be as follows:

...

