Treatment duration is approximately 6 months in the on-demand arm and from approximately 7 (200 days plus screening period of 2-3 weeks) to approximately 19 months in the prophylaxis arm. The maximum treatment period *in the Main Phase of this trial* is ~~24~~ 27 months. In the prophylaxis arm, all patients will continue in the *Main Phase* ~~trial~~ until the last patient *initiated in the prophylaxis arm* has received at least 50 EDs of N8-GP, thus all patients in the prophylaxis arm will receive at least 50 EDs of N8-GP and the average exposure to N8-GP will be more than 1 year. Patients enrolled in pathfinder™ 2 with the intention of entering the pathfinder™ 3 for major surgery can be enrolled in pathfinder™2 after the end of normal recruitment period. For the purpose of defining LPLV, the definition of LPLV *in the Main Phase* excludes these patients and the opening of the Extension Phase will not await these patients to complete 50 EDs in the trial. When *the Main Phase* is completed, all patients will be offered to continue treatment in the Extension ~~trial~~ Phase, if approved by country. As all patients will complete the *Main Phase* at the same time (or within a short timeframe) the transition of patients from *the Main Phase to the Extension Phase*, will be gradual and within a window of approximately 2 months *following the patient's visit schedule*. When the Extension Phase has opened and has been approved in the country the patient must at the next visit end the *Main Phase (Visit 13)* and continue into the *Extension Phase (Visit 14)*.

The distribution of patients *in the Extension Phase of the trial* will be as follows:

The Extension Phase of the trial includes two parts: part 1 and part 2. In part 1, patients who were on prophylaxis treatment every 4 days dosing with N8-GP during the Main Phase of the trial and with a 0-2 bleeding episodes during the last 6 months (180 days) before entering the Extension Phase, will be offered to be randomised to every 7 days or every 4 days treatment (2:1 randomisation). Patients with 3 or more bleeding episodes within the last 6 months of the Main Phase before entering the Extension Phase as well as patients with low bleeding rates who are unwilling to be randomised will continue with the same treatment regimen as in the Main Phase of the trial. Recruitment into the randomisation sub-group in the Extension Phase part 1 will stop

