3.1.4 Risk and Benefits

...

The burden of disease with current FVIII prophylaxis treatment is high – long-term, intra-venous injections, several times a week. Identifying patients that could have adequate bleeding protection with a once weekly injection would be an important break-through for FVIII treatment and could potentially improve the uptake of prophylaxis.

In the extension part 1, patients with a low bleeding rate on every 4 day prophylaxis in the main phase have the possibility of being randomised to once weekly dosing. It cannot be excluded that patients changing from every 4 day prophylaxis to every 7 day will have a risk of more frequent break-through bleeding episodes. Therefore specific rules for switching patients back to every 4 day dosing and for closing the every 7 day treatment arm are included (see section 5.3.1).

5 Trial Design

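### The numerical rule for closing the every-7-day arm in Extension Phase part 1 is defined only for 30 or more randomised patients, and the plan does not commit to that number

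*Protocol*

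**What the plan says.** The closing rule is in Protocol 5.3.1, Extension Phase part 1, added by Amendment 14. It applies "If at least 15 out of 30 patients (or 50% of 30 or more) whom have been randomised" to every 7 days have been switched back. The arm is then closed and the remaining patients move to every 4 days. The amendment's introduction says the rule answers a regulatory concern about break-through bleeding. Section 3.1.4 cites it as a safeguard: "specific rules for switching patients back to every 4 day dosing and for closing the every 7 day treatment arm are included".

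Entry to the randomised group is described in Protocol 5.1 (Amendment 13). Eligibility rests on the number of "bleeding episodes during the last 6 months (180 days) before entering the Extension Phase", which must be no more than two on every-4-day prophylaxis. Those who qualify "will be offered to be randomised to every 7 days or every 4 days treatment (2:1 randomisation"). It is optional: "patients with low bleeding rates who are unwilling to be randomised will continue with the same treatment regimen". Amendment 18 (29 November 2013) stops this recruitment at about April 2014. Neither document gives a target, minimum or expected number for the group, and SAP 2.1 covers sample size for the pivotal part only. The pool is the Main Phase prophylaxis completers, "105 (145) (see section 18.5) patients in prophylaxis treatment", the larger figure applying only if estimated over-dispersion exceeds 6 (Protocol 18.5).

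The same part of 5.3.1 has a patient-level rule: "A patient on every 7 day prophylaxis must be switched back to every 4 day prophylaxis if either of the following criteria are met" within 8 weeks, namely two or more spontaneous bleeds or one severe bleed needing hospital admission. The investigator may also switch a patient at any time.

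Protocol 6.5 requires withdrawal from the trial for, among other reasons, "Haemostasis not achievable with N8-GP: The bleed cannot be controlled after 48 hours using adequate doses of N8-GP".

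**The concern.** Both branches of the closing rule start at 30 patients on every 7 days. With 2:1 allocation that means about 45 volunteers. If the calendar date arrives with 29 or fewer on every 7 days, the wording gives no denominator to which the rule applies, whatever share of them has been switched back. No other numerical rule closes this arm: Protocol 12.5.3 puts enrolment on hold for inhibitors or a related death, and section 12.5.2 states that there is no data monitoring committee. The safeguard described in 3.1.4 could therefore be inoperative in the phase it was written for.

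The count raises a second, smaller question. The numerator is patients switched back to every 4 days. A randomised every-7-day patient withdrawn from the trial under the 6.5 criterion quoted above stays in the denominator but is not switched back. The efficacy analysis treats the two alike: SAP 2.10 handles switchers as withdrawals and imputes bleeds for both.

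**Working it through.** **1. Check of the inputs.** The plan's power figure confirms how it uses rate and over-dispersion (OD). Protocol 18.1 states 79% for 120 patients, a rate of 7.0 per year and OD 5. Power = Φ((8.5 − 7.0)/√(7.0 × 5/120) − 1.96) = Φ(2.78 − 1.96) = 79.3%. The other four rows of that table also reproduce: 89.1%, 97.0%, 87.4% and 71.8%, against 89%, 97%, 87% and 72%.

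**2. Share of patients eligible.** Inputs are 6.8 bleeds per year, OD 5 at about 12 months (Protocol 18.1), and the protocol's rule for scaling OD with exposure (18.5). Assumption: gamma-Poisson (negative binomial) counts.
- Mean in 180 days: 6.8 × 180/365.25 = 3.35.
- OD at 180 days: 1 + (5 − 1) × 180/365.25 = 2.97.
- Shape: 3.35/(2.97 − 1) = 1.70.
- P(0) + P(1) + P(2) = 0.157 + 0.177 + 0.159 = 0.493.

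**3. Number on every 7 days.** Completers × share eligible × acceptance × 2/3.
- 105 completers, OD 5: 105 × 0.493 = 51.7 eligible; × 2/3 = 34.5 at full acceptance. Acceptance needed for 30 on average: 30/34.5 = 87%.
- 145 completers, OD 6: share eligible 0.513; 145 × 0.513 = 74.4; × 2/3 = 49.6. Acceptance needed: 30/49.6 = 60%.

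**4. Chance of reaching 30.** Binomial; the ranges cover exact 2:1 blocks and simple 2:1 allocation. The acceptance rates are assumptions.

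| Completers, OD | Acceptance | Expected on every 7 days | P(30 or more) |
|---|---|---|---|
| 105, OD 5 | 100% | 34.5 | 0.85-0.92 |
| 105, OD 5 | 90% | 31.0 | 0.62-0.66 |
| 105, OD 5 | 80% | 27.6 | 0.27-0.33 |
| 105, OD 5 | 70% | 24.1 | 0.05-0.11 |
| 145, OD 6 | 70% | 34.7 | 0.85-0.91 |
| 145, OD 6 | 60% | 29.8 | about 0.51 |
| 145, OD 6 | 50% | 24.8 | 0.08-0.15 |

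**5. Sensitivity.** With 105 completers, required acceptance is 94% at rate 7.0 and OD 4, and 78% at rate 6.0 and OD 5. Patients on twice-weekly dosing, surgery patients and late country approvals of the extension are not modelled.

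**6. What the wording does below 30.** Suppose 60% of every-7-day patients truly need switching back.

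| Number on every 7 days | Rule as written | 15 switches at any number | 50% of the number randomised |
|---|---|---|---|
| 20 | 0 | 0.13 | 0.87 |
| 25 | 0 | 0.59 | 0.85 |
| 30 | 0.90 | 0.90 | 0.90 |

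The third column is a lenient reading that the text does not state. The fourth applies the sponsor's own proportion once, to the final number, for comparison only.

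**7. The count.** As a purely hypothetical illustration, 12 switches and 3 withdrawals for uncontrolled bleeds among 30 would be 15/30 = 50% leaving the regimen, while the rule would register 12/30 = 40%.

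**The case against.** The strongest reply is that patients are protected without the arm-level rule. The patient-level switch-back is mandatory, works at any number randomised, and the sponsor monitors adherence to it. Amendment 15 adds visits every 4 weeks for the first four months. The Safety Committee (Protocol 12.5.1) may act on any signal, and the sponsor may stop part of the trial at any time (section 20). All of this stands. A reader might infer that part 1 can run with no safeguard against frequent bleeding on every 7 days; the documents do not support that. What is missing below 30 is only the numerical trigger for the arm as a whole.

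A reader might also infer that the plan's assumptions predict a shortfall. They do not. At full acceptance they give 34.5 on every 7 days, with an 8-15% chance of falling below 30 with 105 completers. Any larger risk rests on an acceptance rate that the documents do not contain, and a bleeding rate below 6.8 would enlarge the pool.

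A minimum denominator is a reasonable design choice, because it avoids closing an arm on very few patients. That also stands. Applying 50% after each patient from the first would close the arm about 40% of the time at a true switch rate of only 20%: 0.2 + 0.8 × (0.2/0.8) = 0.40. Applied once to 34 patients, the chance is below 0.001. But a minimum does not explain why nothing is said for the case where it is never reached.

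On the count, an uncontrolled bleed is a failure of bleed treatment and need not reflect the dosing interval. It would go too far to say that the most serious failures escape the rule; no frequency of such withdrawals is given. Only the mismatch between the two sections is established.

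**Conclusion.** The gap is real and limited. The closing rule cannot be met if fewer than 30 patients are randomised to every 7 days, and the plan neither commits to 30 nor says what happens below it. That the text is silent below 30 rests on the wording alone. How likely the case is rests on the gamma-Poisson model, the plan's rate and over-dispersion, and an unknown acceptance rate. With 105 completers the margin is thin (34.5 at best, 87% acceptance needed); with 145 it is comfortable unless acceptance falls to about 60% or lower. The consequence is loss of the one numerical arm-level trigger that 3.1.4 presents as being in place, while patient-level protection and discretionary stops remain. The count is a secondary inconsistency between 5.3.1 and 6.5 whose practical size cannot be judged from the documents.

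**What to change.** Reconcile the closing rule in Protocol 5.3.1 with the voluntary, date-limited randomisation in 5.1, so that the sponsor's own criterion can operate on the number actually randomised to every 7 days if randomisation closes below 30. Reconcile the rule's count with 6.5 by stating how a randomised every-7-day patient withdrawn for an uncontrolled bleed is handled. The threshold and any minimum number remain the sponsor's decision, and continuous application from the first patient is not proposed.

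The cost is one or two sentences in 5.3.1. The sponsor already monitors switches, so no new data or staff are needed. The downside is that the arm could close in cases where the current wording would leave it open.

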5.3.2 Treatment of Bleeding episodes

...

Due to individual patient's bleeding pattern during the *main phase of the trial*, an adaptation in dosing regimen to 50 U/kg twice weekly will be permitted at the investigator's discretion.

8 Methods and Assessments

8.1.4 Visit 14-n and EOT Visit- visit in the Extension Phase of the trial

...

When patients randomised in part 1 have completed the part 1, ~~all~~ *remaining* patients can start part 2 at their next visit beginning at visit 17. Skipping visit 15 and/or 16 should be entered with a comment in EDC.

...

Telephone Contact:

It is recommended that a phone call is made to patients *at the 4 or 6-week interval between the site visits*. ~~who have changed prophylaxis treatment regimen approximately 4 weeks or at time which seem appropriate after the change.~~

8.1.6 Unscheduled Visits

...

The following can be performed/reported at an Unscheduled visit:

...

- *Dosing regimen choice or change and reason if change*

10 Interactive Voice/Web Response System (IV/WRS)

...

As a minimum, the system will be used for:

...

- *changing of dosing frequency*

12 Adverse Events, Technical Complaints and Pregnancies

12.1.3 Disease-related Bleeding

...

In case of *a life-threatening event or a fatal outcome*, the bleeding episode must be reported as an SAE.

18 Statistical Considerations

18.5 Interim Analysis

...

All data from the Main Phase of the trial will be analysed and reported when all patients have reached *at least 50 EDs* (except for patients having had surgery as part of pathfinder™ 3), *and all patients have had their first visit after 50 EDs where all planned assessments including inhibitors have been performed. The analysis of the main phase of the trial will be based on all data up to the patient's last visit at this point.* All main conclusions from the trial will be based on this reporting. Furthermore, an interim analysis will be performed when the patients enrolled in the randomised part of the Extension have completed part 1.

Protocol Amendment
No 15
to Protocol, final version 8.0
dated 12 July 2013

pathfinder™ 2

Trial ID: NN7088-3859

**A Multi-national Trial Evaluating Safety and Efficacy,
including Pharmacokinetics, of NNC 0129-0000-1003 when
Administered for Treatment and Prophylaxis of Bleeding in
Patients with Haemophilia A**

Trial phase: 3

Applicable to all countries

Amendment originator:

This ~~confidential~~ document is the property of Novo Nordisk. ~~No unpublished information contained herein may be disclosed without prior written approval from Novo Nordisk. Access to this document must be restricted to relevant parties.~~

Table of contents "Double click to update Table of Content"

	Page
1 Introduction including rationale for the protocol amendment	3
2 Changes	4

1 Introduction including rationale for the protocol amendment

The VHP requested that patients in the every 7 days treatment arm (Q7D) receive the same visit schedule as patients in the every 4 days treatment arm (Q4D) of the Main Study Phase i.e. monthly visits at the start of treatment, followed by visits every second month.

In addition, it was agreed with the VHP to also implement this visit schedule for patients randomised to Q4D in the extension phase part 1. This is to avoid any bias in the randomised arms. Part 1 of the extension is 6 months in duration, therefore monthly visits for the first 4 months have been introduced, followed by a visit 2 months later.

The VHP stipulated that this visit schedule should apply for every switch to Q7D independent of the part of the extension phase. Therefore, this requirement has also been implemented for Q7D patients in Part 2 of the extension. In Part 2, those switching to Q7D, will have visits every month for the first 4 months and subsequently every two months while on Q7D.

- Therefore the flowchart table 2-3 in section 2 describing the extension phase has been updated to describe this
- Section 5.3.1 has been updated accordingly
- The text regarding telephone contacts has been deleted in Table 2-3 and section 8.1.4 since more often visits has been added instead
- The trial figure 8-2, section 8 and section 8.1.4 describing the visits in extension phase has been revised.

In this protocol amendment:

- Any new text is written *in italics*.
- Any text deleted from the protocol is written using ~~strike through~~

2 Changes

Table 2-3 Flow Chart for Patients on Prophylaxis and On-Demand Treatment in Extension Phase

	Part 1						Part 2		
		14 ^{1,5}	15	16	17 ^{1,5}	18 ^{1,1,5}	12w ²	EOI	
Visit number	-		8w ²	16w ²	24w ²	12w ²	12w ²	Follow-up	-
Time of visit	Weeks							Un-scheduled Visit ^{1,4}	-
Visit window	Weeks								-
Informed Consent		*	-	-	-	-	-		-
Randomisation considerations		*							-
Withdrawal criteria		-	*	*	*	*	*		*
Concomitant medication		-	*	*	*	*	*		*
Date and time of last coagulation factor administration		-	*	*	*	*	*		*
EFFICACY		-	-	-	-	-	-		-
Bleeding episodes (rating severity)		-	*	*	*	*	*		*
SAFETY		-	-	-	-	-	-		-
Adverse events		-	*	*	*	*	*		*
EKG		-	-	-	*	*	*		*
Physical examination		-	-	-	*	*	*		*
Vital signs		-	*	*	*	*	*		*
Antibodies		-	-	-	-	-	-		-
FVIII inhibitors^{7,8}		-	*	*	*	*	*		*
N8-GP-binding antibodies^{7,8}		-	*	*	*	*	*		*

Visit number	Weeks	Part 1					Part 2			Follow-up	Un-scheduled Visit ¹⁴
		14 ¹⁵	15	16	17 ¹⁵	18 ^{14,15}	12w ²	EQI	12w ⁴		
Time of visit	Weeks	same date as V13	8w ²	16w ²	24w ²	12w ²	12w ⁴	12w ⁴			
Visit window	Weeks	-	±2	±2	±2	±2	±2	±2	-	-	
Administration of trial product ¹⁰	-	*	*	*	*	*	*	*	-	*	
Drug accountability	-	-	*	*	*	*	*	*	-	*	
IV/IVRS call	-	*	*	*	*	*	*	*	-	*	
Dispensing trial product	-	*	*	*	*	*	*	*	-	*	
Dosing regimen change	-	*	*	*	*	*	*	*	-	*	
Dispensing trial card	-	*	-	-	-	-	-	-	-	-	
REMINDERS	-	-	-	-	-	-	-	-	-	-	
Affirmation statement	-	-	-	-	-	-	-	-	*	-	
End of trial	-	-	-	-	-	-	-	-	*	-	
eDiary training	-	*	*	*	*	*	*	*	-	*	
eDiary data review	-	-	*	*	*	*	*	*	-	*	
Home treatment training	-	*	*	*	*	*	*	*	-	*	

Footer	Description
1	n = visit number from 19 and onwards
2	weeks after Visit 14
3	weeks apart
4	weeks since last visit
5	Only in case of expected unexpected allergic/anaphylactic reaction
6	Only every second visit (V19, V21, V23, ...)

7	Antibody sample will only be drawn from patients in the on-demand arm if they received treatment since last visit
8	A wash-out period of minimum 96 hrs is needed before the sample
9	Trough to be sampled before dosing and recovery to be sampled 30 min (\pm 5 min) after dosing, only for prophylaxis patients
10	Only for patients in prophylaxis treatment
11	Only height every year for patients below 18 years, otherwise only BW
12	Only yearly (at V21, V25...)
13	Only to be taken if HIV status is positive
14	Assessment during unscheduled visit are not mandatory but can be performed
15	It is recommended to contact patients by phone at the 4 and 6-week interval between the site visits (see section 8.1.4)

	Extension Part 1							Extension Part 2						
	14	14a	15	15a	16	17	Visit number	17 ^a	18	18 ^a	19 ^a -n ² / 19 ^b -n ²	EOT	Follow-up	Un-scheduled Visit ⁴
Visit number	14	14a	15	15a	16	17		17 ^a	18	18 ^a	19 ^a -n ² / 19 ^b -n ²	EOT	Follow-up	Un-scheduled Visit ⁴
Non-randomised PPX/ On-Demand patients Time of visit (weeks)	same date as V13	-	8w ¹	-	16w ¹	24w ¹	Q4D, Twice weekly PPX/ On-demand	-	12w±2 ³	-	12w±2 ³	12w±2 ³		
Randomised PPX patients Time of visit (weeks)	same date as V13	4w±1 ¹	8w±1 ¹	12w±1 ¹	16w±1 ¹	24w±1 ¹	Q7D PPX	4w±1 ³	8w±1 ³	4w±1 ³	8w±1 ³ / 4±1	8w±1 ³ / 4±1		
Informed Consent	x													
Randomisation considerations	x													
Withdrawal criteria		x	x	x	x	x		x	x	x	x	x		x
Concomitant medication		x	x	x	x	x		x	x	x	x	x		x
Date and time of last coagulation factor administration		x	x	x	x	x		x	x	x	x	x		x
EFFICACY														
Bleeding episodes (rating severity)		x	x	x	x	x		x	x	x	x	x	x	x
SAFETY														
Adverse events		x	x	x	x	x		x	x	x	x	x	x	x
ECG											x ²	x		x
Physical examination											x ⁶	x		x

Visit number	Extension Part 1							Extension Part 2					
	14	14a	15	15a	16	17	17a ⁴	18	18a ⁴	19a-n ² / 19a-n ²	EOT	Follow-up	Un-scheduled Visit ⁴
Non-randomised PPX/ On-Demand patients Time of visit (weeks)	same date as V13	-	8w ¹	-	16w ¹	24w ¹	-	12w±2 ³	-	12w±2 ³	12w±2 ³		
Randomised PPX patients Time of visit (weeks)	same date as V13	4w±1 ¹	8w±1 ¹	12w±1 ¹	16w±1 ¹	24w±1 ¹	4w±1 ³	8w±1 ³	4w±1 ³	8w±1 ³ / 4±1	8w±1 ³ / 4±1		
Dispensing trial card	x												
REMINDEES													
Affirmation statement											x	x	
End of trial											x	x	
eDiary training	x	x	x	x	x	x	x	x	x	x			x
eDiary data review		x	x	x	x	x	x	x	x	x	x		x
Home treatment training	x	x	x	x	x	x	x	x	x	x			x

Footer	Description
1	weeks after Visit 14
2	n = additional visit number until end of trial
3	weeks since last visit
4	It is mandatory to attend 2 consecutive a-visits upon switching to every 7 day treatment regimen in order to achieve visits every 4 weeks (± 1 week) during the first 4 months. After this time period the patient must attend visits every 8 weeks (± 1 week) while on every 7 day treatment regimen.
5	Only in case of expected unexpected allergic/anaphylactic reaction
6	Only every second non a-visits, e.g. visit (V19, V21, V23...)
7	Antibody sample will only be drawn from patients in the on-demand arm if they received treatment since last visit
8	A wash-out period of minimum 96 hrs is needed before the sample
9	Trough to be sampled before dosing and recovery to be sampled 30 min (± 5 min) after dosing, only for prophylaxis patients
10	Only for patients in prophylaxis treatment
11	Only height every year for patients below 18 years, otherwise only BW
12	Only yearly (at V21, V25...)
13	Only to be taken if HIV status is positive
14	Assessment during unscheduled visit are not mandatory but can be performed

5 Trial Design

...

